**Comparative Study on the Efficacy of High-Definition Electronic
Amplification Endoscopy Combined with Image Enhancement
Technology and Colposcopy in the Exploration of Cervical and
Vaginal Pathologies**
Research protocol

Project leaders:	Contact number:
Version: V2.0	Version date: March 4, 2026

I. Research Background

Colposcopy is currently an essential examination method for detecting cervical and vaginal lesions. However, traditional colposcopy has low magnification and limited field of view, resulting in limited identification of early cervical lesions. According to existing research reports, the diagnostic accuracy of colposcopy for low-grade lesions is only approximately 43.4%, while for high-grade lesions it ranges from 59% to 76%. High-definition magnified electronic endoscopy (100–150x) can clearly visualize microvessels and mucosal structures. In recent years, gastrointestinal magnified endoscopy combined with image enhancement techniques (e.g., NBI/BLI/LCI) has established a mature vascular and epithelial interpretation system for early esophageal squamous cell carcinoma diagnosis. The cervical, vaginal, and esophageal tissues share similar pathological evolution patterns of precancerous lesions and early carcinogenesis due to their stratified squamous epithelium. Theoretically, this technical system can be extended to the exploration of lower genital tract lesions. Preliminary single-center, small-sample studies in Japan suggest that this technology demonstrates superior diagnostic performance for high-grade cervical lesions compared to traditional colposcopy, but high-quality clinical validation remains lacking domestically. Therefore, this study aims to systematically evaluate the diagnostic efficacy of high-definition magnified electronic endoscopy combined with image enhancement techniques versus traditional colposcopy through rigorous paired diagnostic trial design, aiming to

provide clinicians with a more precise examination tool to address the limitations of current methods. The goal is to establish an endoscopic atlas for cervical and vaginal lesions and improve diagnostic accuracy.

II. Research Objective

1. Primary research objective: To compare the diagnostic accuracy of high-definition electronic magnification endoscopy combined with image enhancement technology versus colposcopy in detecting cervical and vaginal lesions.

2. Secondary research objectives: To evaluate and compare the sensitivity, specificity, positive predictive value, and negative predictive value of the two examinations, and to assess differences in imaging characteristics (e.g., lesion boundary clarity and microvascular structure visualization) between the two methods.

3. Research hypothesis: High-definition electronic magnification endoscopy combined with image enhancement technology demonstrates superior diagnostic accuracy for cervical and vaginal lesions compared to traditional colposcopy.

III. Research Content

3.1 Study Design

Study type: Paired diagnostic test design (diagnostic accuracy study with intra-participant comparisons)

Randomization method: sequential randomization

Blind method: Open (blinding of personnel interpreting pathological diagnostic results)

3.3 Study duration: March 2026 – March 2030

3.4 Sample Size and Calculation Basis

Based on research reports, the diagnostic accuracy of colposcopy for low-grade lesions is only approximately 43.4%, while the diagnostic accuracy for high-grade lesions ranges from 59% to 76%. A domestic multicenter study demonstrated that traditional colposcopy has a specificity of 75.1% and a sensitivity of 70.2% in detecting high-grade cervical lesions. Control group indicators (P0): According to data, traditional colposcopy achieves a diagnostic accuracy of approximately 59-76% for high-grade lesions (HSIL+). The lower limit of 59% is adopted as the calculation benchmark. Experimental group expected indicators (P1): It is hypothesized that high-definition magnified electronic colposcopy can significantly improve detection rates. A 20-percentage-point improvement is required to achieve statistically significant clinical significance, with diagnostic accuracy potentially reaching around 79%. Prevalence in target population: Literature reports indicate that among participants undergoing colposcopy, the proportion of cases ultimately pathologically confirmed as high-grade lesions (HSIL+) ranges from 20% to 40%, with a set threshold of 30%. Statistical power (Power, $1-\beta$): Set at 90%, with $\alpha = 0.05$ (two-tailed).

Methods: Sample size estimation was performed using the sample size calculation formula for paired design diagnostic tests (McNemar test). A minimum of 212 study participants with complete paired data and valid gold standard results were required, accounting for a dropout rate of 10%-20%. The final planned total sample size was 270 cases.

Continuous enrollment was employed to include all eligible participants who met the inclusion criteria and consented to participate in the study until the target sample size was achieved. To balance potential biases arising from examination

sequence, a simple randomization method was used to assign participants to two distinct examination sequences (Sequence A group: initial observation and image acquisition using a conventional optical colposcope (magnification 7.5-15x), followed by endoscopy (preset magnification 90-120x); Sequence B group: initial examination using an endoscope, followed by colposcopy).

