3.8 Data Management and Statistical Analysis

Data collection: Structured electronic case report forms were designed and implemented for data acquisition, covering baseline characteristics, imaging features and proposed diagnoses of the two examinations, biopsy information and pathological results, follow-up records, and adverse event profiles.

Data entry and verification: Independent entry by two individuals, employing logical consistency checks and scope verification, with disputed data corrected based on original records.

When baseline measurement data conform to normal distribution, mean \pm standard deviation is used for description, and independent samples t-test is

employed for intergroup comparisons. If normal distribution is not met, median (interquartile range) is used for description, and Mann-Whitney U test is applied for intergroup comparisons. For baseline categorical data, case count (percentage) is used for description, and chi-square test or Fisher's exact test is utilized for intergroup comparisons.

Primary outcome measures: The accuracy rates of both examinations were calculated separately as (true positives + true negatives) / total cases. The difference in accuracy rates between the two examinations was compared using a paired chi-square test to determine statistical significance, with the calculated difference and its 95% confidence interval (CI) reported. Sensitivity and specificity were assessed using the McNemar test. For secondary outcome measures, count data comparisons between groups were performed using chi-square tests, with rate differences and their 95% CIs reported. When data followed a normal distribution, independent samples t-tests were used for intergroup comparisons. For non-normally distributed metric data, Mann-Whitney U tests were employed for intergroup comparisons.

The incidence rate of adverse events was calculated as the total incidence rate and the incidence rates of various events, with chi-square test or Fisher's exact test used to compare intergroup differences.

Subgroup analysis was performed to evaluate the stability of the results, with all findings presented as two-sided. A p-value <0.05 was considered statistically significant.

4、Alternative diagnostic and therapeutic methods available

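### The 90% power in section 3.4 is built on accuracy for HSIL+, not on the overall accuracy that is the primary outcome, and 212 does not follow for that outcome

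*Protocol*

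**What the plan says.** Protocol section 3.1 describes a "Paired diagnostic test design (diagnostic accuracy study with intra-participant comparisons"), so each woman has both examinations.

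Section 3.4 takes its control value from the statement that "traditional colposcopy achieves a diagnostic accuracy of approximately 59-76% for high-grade lesions (HSIL"+). It then says "The lower limit of 59% is adopted as the calculation benchmark" and sets the endoscopy value 20 points higher, at about 79%. It introduces that difference with the words "A 20-percentage-point improvement is required to achieve statistically significant clinical significance". It adds an HSIL+ prevalence of 30% (literature range 20% to 40%), 90% power and two-sided alpha 0.05, and names the McNemar formula. The result is "A minimum of 212 study participants with complete paired data and valid gold standard results were required", raised to 270 for 10% to 20% dropout. No discordant proportion or correlation is given, and the use made of the prevalence is not explained.

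The same section also reports that "traditional colposcopy has a specificity of 75.1% and a sensitivity of 70.2% in detecting high-grade cervical lesions".

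Section 3.7 makes the accuracy rate of the two examinations primary. Section 3.8 defines it as ("true positives + true negatives) / total cases" and compares the examinations with a paired chi-square test.

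**The concern.** The sample-size paragraph and the primary analysis appear to concern different quantities. Accuracy for HSIL+, combined with a prevalence, is how one sizes a comparison within diseased women: find the number of cases needed, then divide by prevalence. Overall accuracy counts every woman, and prevalence does not enter its McNemar formula once the two accuracies and the discordance are fixed.

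If so, the 90% describes a comparison that the trial does not treat as primary, and the power of the primary test is not stated. The distinction matters because a gain confined to HSIL+ women is diluted in overall accuracy: 20 points in 30% of the sample is 6 points overall if specificity is unchanged.

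**Working it through.** **Inputs.** All are from section 3.4: P0 = 0.59, P1 = 0.79, so d = 0.20; prevalence 0.30; two-sided alpha 0.05 (z = 1.96); power 90% (z = 1.2816); 212 pairs. The discordant proportion ψ is not given, so its whole feasible range is used:

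- minimum: ψ = d = 0.20
- independent errors: 0.59 × 0.21 + 0.79 × 0.41 = 0.4478
- maximum (no woman misclassified by both examinations): 0.41 + 0.21 = 0.62

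**Formulas.** n = [1.96√ψ + 1.2816√(ψ − d²)]² / d². Power = Φ{(√n·d − 1.96√ψ) / √(ψ − d²)}.

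**Attempt to reproduce 212.**

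| ψ | Pairs needed, all women | Same, divided by 0.30 | Power, 212 pairs | Power, 63.6 HSIL+ women |
|---|---|---|---|---|
| 0.20 | 48.2, so 49 | 161 | >99% | 96% |
| 0.258 | 63.5, so 64 | 212 | >99% | 90% |
| 0.4478 | 113.4, so 114 | 378 | 99% | 67% |
| 0.62 | 158.7, so 159 | 529 | 96% | 53% |

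For example, at ψ = 0.62: (1.96 × 0.7874 + 1.2816 × 0.7616)² / 0.04 = 2.519² / 0.04 = 158.7.

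For all women, solving n = 212 gives ψ = 0.82, which exceeds the maximum of 0.62. No feasible discordance therefore gives 212 with 90% power for 59% versus 79% in overall accuracy. In HSIL+ women, 212 × 0.30 = 63.6, and n = 63.6 solves to ψ = 0.258. That value is feasible but not stated.

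An unpaired two-proportion formula comes close: 2 × 107.1 = 214. It is not the named method, and a paired design does not add two arms.

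The dropout step is sound: 212 / 0.80 = 265, which 270 covers.

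**The other colposcopy figures in section 3.4.** If accuracy is judged at a binary HSIL+ threshold (an assumption), sensitivity 70.2% and specificity 75.1% at 30% prevalence give 0.3 × 0.702 + 0.7 × 0.751 = 0.736. The range is 0.731 to 0.741 for prevalence 40% to 20%. This differs from 0.59 by about 15 points.

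**What 212 pairs can detect from 73.6% with 90% power.** Here ψ follows from the two accuracies and the correlation r between correct classifications: ψ = p0(1 − p1) + p1(1 − p0) − 2r√[p0(1 − p0)p1(1 − p1)].

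- r = 0: 12.6 points
- r = 0.3: 10.8 points
- r = 0.5: 9.3 points
- ψ = d, the least possible: 4.9 points

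**If the 20 points apply to HSIL+ women only.** With specificity unchanged at 75.1%, d = 0.3 × 0.20 = 0.06. With independent errors in both strata, ψ = 0.3 × 0.4478 + 0.7 × 2 × 0.751 × 0.249 = 0.396, and power at 212 is 28%. With the least discordance, ψ = 0.06, it is 95%.

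**Smallest observed difference significant at 0.05 with 212 pairs.** 1.96√(ψ/212) is 6.0 points at ψ = 0.20, 9.0 at 0.4478 and 10.6 at 0.62.

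**The case against.** **212 can be reached.** A calculation in HSIL+ women with discordance near 0.26 uses every stated input, including the otherwise idle prevalence. This stands. A reader might infer an arithmetic error, but the documents do not support that: 212 is underdetermined, and a statistical analysis plan could supply the missing discordance. What such a plan could not do is make 212 with 90% power fit overall accuracy at 59% versus 79%.

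**59% may mean accuracy at the HSIL+ threshold in all women.** The wording allows this, and the quantity would then be of the right type. The requirement would be at most 159 pairs, the prevalence would have no role, and power at 212 would be at least 96%. The 90% still does not match.

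**73.6% is not the protocol's benchmark.** Correct. It rests on one cited study of cervical lesions and on a binary threshold, whereas the trial covers cervical and vaginal lesions. Section 3.4 also quotes 43.4% accuracy for low-grade lesions. A crude grade-specific illustration, applying that to all women without HSIL+, gives 0.3 × 59% + 0.7 × 43.4% = 48%. The 73.6% is therefore only an assumption that the sponsor should confirm or replace.

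**The trial looks underpowered.** A reader might set 79% against 73.6% and conclude that a 5.4-point gain will be missed. The protocol never hypothesises that pair, and power for it at 212 runs from 25% (independent errors) to 93% (least possible discordance). For a true 20-point gain in overall accuracy, 212 pairs are more than enough.

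**The 20-point sentence is a translation.** It plausibly means the target difference. That is a reason to reword it, and the point is minor.

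**Conclusion.** The point holds in this form: section 3.4 attaches 90% power to a quantity that its wording and its use of prevalence place in HSIL+ women, while the primary outcome is overall accuracy in all participants. With the stated inputs and the named test, 90% power for the primary outcome needs 49 to 159 pairs, not 212. The figure 212 is recovered only with 63.6 HSIL+ women and an unstated discordance of about 0.26.

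The conclusion rests on the standard normal-approximation McNemar formula and on the full range of discordance that 59% and 79% allow. It does not depend on the 73.6% figure.

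Nothing here shows that the trial is too small. The power of the primary test could be low or well above 90%, depending on the true overall gain and on the discordance, and section 3.4 fixes neither for the primary outcome. The statement should be corrected because the size of the primary comparison is justified by it.

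**What to change.** Keep N = 270 and rewrite the sample-size paragraph of section 3.4:

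1. State P0 and P1 for overall accuracy as defined in section 3.8. Reconcile 59% with the 70.2% sensitivity and 75.1% specificity in the same section. If 73.6% is used, label it as an assumption (binary HSIL+ threshold, 30% prevalence).
2. State the assumed discordance or correlation, and show the calculation.
3. Replace the power claim with the gain in overall accuracy that 212 pairs detect with 90% power: for example about 9 to 13 points from 73.6% at correlation 0.5 to 0, and less at higher correlation.
4. If sensitivity for HSIL+ is also to be powered, say so separately. About 64 HSIL+ women give 53% to 96% power for 59% versus 79% over the feasible discordance: 67% with independent errors, and 90% only at about 0.26.
5. Reword the 20-point sentence as the assumed target difference. It is not a condition for statistical significance, since with 212 pairs an observed difference of about 6 to 11 points is already significant.

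The cost is one rewritten paragraph, with no extra participants and no change to procedures or the primary test. The downside is that the stated power may become less favourable.

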3.5 Inclusion and exclusion criteria, withdrawal/termination criteria

Inclusion criteria: ① Age 18-65 years with indications for colposcopy (HPV16/18 positive; HPV non-16/18 positive with LCT \geq ASCUS; HPV negative with LCT \geq LSIL; persistent HPV infection \geq 1 year). ② Voluntary signing of informed consent form.

Exclusion criteria: ① Pregnant or lactating women. ② Acute genital tract infections or severe coagulation disorders. ③ History of radiotherapy for malignant tumors or severe mental disorders in study participants. ④ Minors.

Exit criteria: ① Requested withdrawal by study participants. ② Occurrence of serious adverse events (e.g., major bleeding, allergic reactions).

3.6 Methods and Procedures

The same study participant was randomly assigned to groups A and B according to sequence randomization, with examination sequences conducted in two groups.

Procedure for Evaluation Method 1 (Colposcopy): Study participants were placed in the lithotomy position. After routine disinfection and draping, a speculum was inserted. Traditional colposcopy was performed at designated time points (after saline administration, 1 minute and 2 minutes post-acetic acid test, and post-iodine test). The colposcopy specialist interpreted imaging features, recorded proposed diagnostic opinions, and marked suspected lesion sites (denoted as Point Y). The cervical surface was conceptualized as a clock face centered on the cervical os, with

the 12 o'clock position representing the top of the cervix. For example, Y6 indicates suspected cervical lesion at the 6 o'clock position under colposcopy.

[figure not shown]
Evaluation of Probe Method 2 (High-Definition Electronic Magnification Endoscopy + Image Enhancement Technology): Procedure Flow: In the same study participants, high-definition electronic magnification endoscopy combined with image enhancement technology was used to observe the cervix and vagina and acquire images at specified time points (after saline administration, 1 minute after acetic acid test, 2 minutes after acetic acid test, and after iodine test). The endoscopist interpreted the images based on characteristic features, recorded proposed diagnostic opinions, and marked suspicious lesion sites on the schematic diagram (denoted as N-point, e.g., N3 indicates suspected cervical lesion at point 3 under endoscopic evaluation; lesions simultaneously identified as suspicious by colposcopy and endoscopy are labeled as T-point, e.g., T9 indicates suspected cervical lesion at point 9 according to both examinations).

Biopsy specimens from suspicious sites (2-4 mm per tissue block, totaling 2-4 tissue blocks) were submitted for examination. Endoscopists and colposcopists were unaware of each other's interpretation results. Pathologists conducted microscopic examination of the biopsy specimens and issued pathological diagnosis results (pathologists were unaware of the grouping and proposed microscopic diagnosis results).

For study participants who showed no suspicious lesions on conventional colposcopy or endoscopy, informed consent was obtained to voluntarily opt for biopsy. Those who chose biopsy had their pathological results compared with the proposed microscopic diagnosis using the gold standard. Participants opting against biopsy underwent 6-12 month follow-up HPV and TCT testing. Those with negative follow-up HPV/TCT results, abnormal HPV/TCT findings, or persistent negative results after colposcopy evaluation or colposcopic biopsy pathology were classified

as true negatives (suboptimal microscopic diagnosis negative with follow-up gold standard confirmation). Participants with \geq CINII or VAINII findings after 6-12 month colposcopic biopsy were categorized as false negatives (no suspicious lesions detected microscopically but confirmed high-grade lesions by follow-up gold standard). Image feature analysis was performed between experimental and control groups, with accuracy validated through pathological or follow-up results. Adverse events were recorded 24 hours post-examination (when vaginal swabs were removed after biopsy) for participants undergoing both instrument-based examinations.

technology roadmap :

3.7 Evaluation indicators:

Primary outcome measure: accuracy rates of the two examinations, with histopathological results or follow-up outcomes serving as the gold standard.

Secondary outcome indicators: sensitivity, specificity, positive predictive value, negative predictive value, AUC, and lesion recognition rate (referring to the ability to identify suspicious lesions through high-definition magnified endoscopy in cases that are difficult to detect with conventional colposcopy).

Efficacy indicators: clarity of lesion margins and visualization capability of microvascular structures (including resolution of point-like, clustered, and spiral patterns), assessed using a 4-point Likert scale: 1=poor, 2=average, 3=good, 4=excellent.

Safety indicators: Examination-related adverse event incidence rate (e.g., bleeding, infection, mucosal injury or perforation during the procedure), postoperative complication rate within 24 hours (e.g., lower abdominal discomfort, vaginal bleeding, fever), and examination tolerance (assessing the proportion of study participants who discontinued the examination midway or requested termination of the procedure).

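### The true-negative rule in section 3.6 overlaps the false-negative rule and lets a negative repeat colposcopy without histology confirm a negative; this inflates both tests' absolute rates but not the paired comparison.

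*Protocol*

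**What the plan says.** The objective in Protocol section II is "To compare the diagnostic accuracy of high-definition electronic magnification endoscopy combined with image enhancement technology versus colposcopy in detecting cervical and vaginal lesions", so conventional colposcopy is the comparator. The primary outcome in section 3.7 is "accuracy rates of the two examinations, with histopathological results or follow-up outcomes serving as the gold standard". Section 3.8 computes accuracy as true positives plus true negatives over total cases, so the true-negative definition feeds the primary numerator directly.

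Section 3.6 gives the reference standard for test-negative women:

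- Index biopsy is optional: "For study participants who showed no suspicious lesions on conventional colposcopy or endoscopy, informed consent was obtained to voluntarily opt for biopsy".
- Women who decline are followed: "Participants opting against biopsy underwent 6-12 month follow-up HPV and TCT testing".
- The true-negative class is given by this list: "Those with negative follow-up HPV/TCT results, abnormal HPV/TCT findings, or persistent negative results after colposcopy evaluation or colposcopic biopsy pathology were classified". The label attached to every item on it reads "as true negatives (suboptimal microscopic diagnosis negative with follow-up gold standard confirmation".
- The false-negative class is CINII/VAINII or worse, worded as "findings after 6-12 month colposcopic biopsy were categorized as false negatives".

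Section 3.4 gives colposcopy a sensitivity of 70.2% and a specificity of 75.1% for high-grade lesions, and sets HSIL+ prevalence at 30%.

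**The concern.** The true-negative class is a list of alternatives joined by 'or', and one of them is an abnormal follow-up test. An abnormal result cannot confirm absence of disease. As written, the class also overlaps the false-negative class.

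The sentence may be a garbled way of saying that abnormal follow-up counts as negative once the subsequent work-up is persistently negative. A problem remains on that reading, because the work-up may be a colposcopic evaluation or a colposcopic biopsy. A visual impression is enough, and it comes from the modality under comparison. A lesion that colposcopy missed once can be missed again and then recorded as a correct negative. A false negative requires histology, so the error runs in one direction only.

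At stake are the absolute accuracy, sensitivity and NPV of both tests. These are the figures a clinician would use to judge how far a negative examination reassures.

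**Working it through.** The protocol states no figure for this effect, so there is none to reproduce.

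**Inputs.** From section 3.4: N = 270, prevalence 30% (81 HSIL+, 189 without), colposcopy sensitivity 0.702 and specificity 0.751. Assumed: endoscopy sensitivity 0.79 (the section's expected 79%, treated as a sensitivity) and specificity 0.751. The section 3.6 rule is taken to apply to women negative on both tests.

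**True values under these inputs.**
- Colposcopy accuracy: 0.3 × 0.702 + 0.7 × 0.751 = 73.6%.
- Endoscopy accuracy: 0.3 × 0.79 + 0.7 × 0.751 = 76.3%.
- Difference: 0.3 × (0.79 − 0.702) = 2.6 points.

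**HSIL+ missed by both tests.**
- Independent errors: 81 × 0.298 × 0.21 = 5.1.
- Nested errors (every endoscopy miss is also a colposcopy miss): 81 × 0.21 = 17.0.

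**Mislabelled cases, m.**
- Ceiling: all of these are labelled true negative, so m = 5.1 to 17.0.
- Kinder reading: all decline index biopsy, all have abnormal follow-up and go to repeat colposcopy, and that colposcopy misses 29.8% independently of the first examination. Then m = 0.298 × 5.07 = 1.5 to 0.298 × 17.0 = 5.1.

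**Effect.** Accuracy rises by m/270 for both tests. Sensitivity becomes 56.9/(81 − m) for colposcopy (81 × 0.702 = 56.9) and 64.0/(81 − m) for endoscopy (81 × 0.79 = 64.0).

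| | m | Accuracy, both tests | Colposcopy sensitivity (true 70.2%) | Endoscopy sensitivity (true 79%) |
|---|---|---|---|---|
| Kinder reading | 1.5 to 5.1 | +0.6 to +1.9 points | 71.5% to 74.9% | 80.5% to 84.3% |
| Ceiling | 5.1 to 17.0 | +1.9 to +6.3 points | 74.9% to 88.9% | 84.3% to 100% |

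For NPV, colposcopy has 189 × 0.751 + 81 × 0.298 = 166.1 test-negatives, so its NPV rises by m/166.1: 0.9 to 3.1 points on the kinder reading and 3.1 to 10.2 at the ceiling.

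**Sensitivity to assumptions.** With endoscopy sensitivity 85% and N = 212 (63.6 HSIL+), the ceiling is 63.6 × 0.298 × 0.15 = 2.8 to 63.6 × 0.15 = 9.5 cases, or +1.3 to +4.5 points.

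**The comparison.** A woman negative on both tests is right on both or wrong on both. Relabelling her leaves the discordant counts b and c unchanged, and so also the McNemar test and (b − c)/N. The difference stays at 2.6 points.

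**The denominator.** If k double-negative women without a reference were left out, (b − c)/N would be multiplied by N/(N − k). The extreme case is a 20% loss made up entirely of such women: k = 54, 270/216 = 1.25, and 2.6 points becomes 3.3.

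**The case against.** The strongest reply is that the sentence is poor English rather than a rule anyone would apply literally, and that safeguards stand around it. Women with nothing suspicious are offered an index biopsy. A follow-up biopsy showing CINII/VAINII or worse makes the case a false negative. The repeat colposcopy is a later examination within a composite of HPV, TCT and histology. All of this stands. It rules out saying that the comparator simply serves as its own gold standard, or that missed HSIL+ in general is recorded as correct. Only HSIL+ missed by both tests and biopsied neither at baseline nor at follow-up is affected, so 5 to 17 is a ceiling.

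A reader might infer that the rule tilts the trial towards endoscopy. The documents do not support that: the affected women are concordant, and the test and the accuracy difference are unchanged.

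A reader might also infer from "A minimum of 212 study participants with complete paired data and valid gold standard results were required" that women without a reference will be dropped from the analysis. That sentence sizes the trial and sets no analysis population; section 3.8 divides by total cases. If such women were dropped, mostly true negatives would go, which lowers absolute accuracy. Relabelling every double miss and dropping 54 double-negatives gives endoscopy (205.9 + 5.1 − 54)/216 = 72.7% to (205.9 + 17.0 − 54)/216 = 78.2%, against a true 76.3%. The inflation stated here is therefore that of the labelling rule alone.

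What the reply does not remove is the overlap between the two classes and the acceptance of a colposcopic impression without histology. Both are in the protocol's own wording.

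**Conclusion.** The point holds in this limited form. The rule contradicts the false-negative definition if read literally. If read kindly, it still lets the comparator modality confirm a negative without histology. It overstates the absolute accuracy, sensitivity and NPV of both tests, and leaves the McNemar test and the paired accuracy difference intact.

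The likely size is modest: about 1.5 to 5 of 81 HSIL+, or +0.6 to +1.9 accuracy points, with a ceiling of 5 to 17 cases and +6.3 points. These figures rest on an assumed endoscopy sensitivity of 79%, equal specificities and 30% prevalence. The lower range also assumes repeat misses independent of the first. Correlated misses would raise it, and uptake of index biopsy would lower it.

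**What to change.** Reconcile the two definitions in section 3.6 so that no woman can fall into both:

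- True negative: histology without HSIL+, or follow-up HPV and TCT both negative.
- False negative: HSIL+ on histology, at the protocol's own threshold of CINII/VAINII or worse.
- Abnormal follow-up with only a negative repeat colposcopy: reference not verified, and not a true negative.

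Report absolute accuracy, sensitivity, specificity and NPV with imputation for unverified women, and give all-negative and all-positive bounds as a sensitivity analysis. Compute the paired accuracy difference over all women who had both examinations. Double-negative women are concordant under either label, so they need no reference result for this, and keeping them avoids the inflation of up to 1.25-fold.

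The cost is wording, one added analysis and less precise absolute rates. The bounds could be wide. Double-negatives are 0.3 × 0.298 × 0.21 + 0.7 × 0.751² = 41% to 0.3 × 0.21 + 0.7 × 0.751 = 59% of women, or 112 to 159 of 270. If, as an assumption, 20% to 60% of them had abnormal follow-up without histology, 22 to 95 women would be unverified, and the all-positive bound would lower both accuracies by 8 to 35 points (22/270 to 95/270). The change concerns how collected data are classified; it does not alter who is biopsied or followed, and no additional procedures are needed.

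### The lesion recognition rate is defined for endoscopy only and on unconfirmed lesions, so it cannot favour colposcopy and rises when endoscopy over-calls

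*Protocol*

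**What the plan says.** Section 3.7 of the protocol gives the secondary outcomes as "sensitivity, specificity, positive predictive value, negative predictive value, AUC, and lesion recognition rate". The last of these is glossed as the "ability to identify suspicious lesions through high-definition magnified endoscopy in cases that are difficult to detect with conventional colposcopy". No matching rate is given for colposcopy, and no numerator, denominator, counting unit or criterion for difficulty is stated. The reference standard appears in the line above, attached to the primary outcome: "accuracy rates of the two examinations, with histopathological results or follow-up outcomes serving as the gold standard".

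Section 3.6 shows what suspicious means in this protocol. During the examination the colposcopist "marked suspected lesion sites (denoted as Point Y" and the endoscopist "marked suspicious lesion sites on the schematic diagram (denoted as N-point"; "lesions simultaneously identified as suspicious by colposcopy and endoscopy are labeled as T-point". Histology comes afterwards: "Biopsy specimens from suspicious sites (2-4 mm per tissue block, totaling 2-4 tissue blocks) were submitted for examination".

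For secondary outcomes section 3.8 says that "count data comparisons between groups were performed using chi-square tests, with rate differences and their 95% CIs reported".

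**The concern.** A secondary outcome meant to show added detection should be able to come out either way. This one cannot. A lesion that endoscopy marks where colposcopy struggles adds to it. A lesion that colposcopy marks and endoscopy misses has no place in it, although such sites are recorded as Y points. Because the numerator is suspicious rather than confirmed lesions, every extra site that the endoscopist calls in a difficult case raises the rate, whether or not disease is there.

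The study hypothesis (section II) is that endoscopy is superior. A positive lesion recognition rate could be taken as support for it, yet the rate would be positive for two equally good tests that merely disagree in some women. The rate difference with a 95% CI in section 3.8 needs a figure for each examination, and the definition yields one for endoscopy alone.

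**Working it through.** The protocol gives no expected value for this rate, so there is no figure to reproduce. The check is an illustration of how the definition behaves.

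**Inputs from section 3.4:** colposcopy sensitivity 70.2% and specificity 75.1% for high-grade lesions; HSIL+ prevalence 30% (range 20% to 40%); 212 participants with complete paired data and a valid gold standard.

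**Assumptions not in the protocol:** endoscopy performs exactly as colposcopy does; difficult to detect means colposcopy-negative; counting is by participant.

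**Step 1, strata.** HSIL+: 212 × 0.30 = 63.6. Not HSIL+: 212 × 0.70 = 148.4.

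**Step 2, endoscopy-only calls with independent errors.**
- HSIL+: 63.6 × (1 − 0.702) × 0.702 = 13.3
- Not HSIL+: 148.4 × 0.751 × (1 − 0.751) = 27.8
- Total 41.1, of which 27.8/41.1 = 68% are not HSIL+

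Colposcopy-negative participants number 63.6 × 0.298 + 148.4 × 0.751 = 130.4. The 41 calls are therefore 31% of colposcopy-negatives, or 19% of all 212. The protocol does not say which denominator applies.

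**Step 3, correlated errors.** With equal marginals and within-stratum correlation r, each discordant cell is multiplied by (1 − r).

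| Correlation in HSIL+ / not HSIL+ | Endoscopy-only calls | Share not HSIL+ |
|---|---|---|
| 0 / 0 | 13.3 + 27.8 = 41.1 | 68% |
| 0.5 / 0.5 | 6.7 + 13.9 = 20.5 | 68% |
| 0 / 0.5 | 13.3 + 13.9 = 27.2 | 51% |
| 0.5 / 0 | 6.7 + 27.8 = 34.4 | 81% |
| towards 1 / 1 | towards 0 | – |

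**Step 4, prevalence (independent errors).** At 20%: 8.9 + 31.7 = 40.6 calls, 78% not HSIL+. At 40%: 17.7 + 23.8 = 41.5 calls, 57% not HSIL+.

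**Step 5, over-calling.** Keep endoscopy sensitivity at 70.2%, keep errors independent, and lower only its specificity.

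| Endoscopy specificity | Rate among 130.4 colposcopy-negatives | HSIL+ share of calls |
|---|---|---|
| 75.1% | (13.3 + 27.8)/130.4 = 31% | 32% |
| 60% | (13.3 + 44.6)/130.4 = 44% | 23% |
| 50% | (13.3 + 55.7)/130.4 = 53% | 19% |

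The rate goes up as the test gets worse.

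**Step 6, confirmed and in both directions.** For the equal tests of step 2, confirmed HSIL+ found by endoscopy only is 13.3 and by colposcopy only is also 13.3, a difference of 0. At correlation 0.5 it is 6.7 against 6.7, again 0. The symmetric, confirmed version gives the right answer at either correlation.

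**The case against.** The strongest reply is that the text in section 3.7 is a gloss, not a calculation rule, and that a statistical analysis plan may supply the denominator, the unit and the criterion for difficulty. That is fair for those three items. It does not cover the direction or the unconfirmed numerator, which the protocol's own wording sets.

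A second reply is that yield beyond standard practice is one-directional by nature and can be a legitimate descriptive measure. It can, if the finds are confirmed and it is not presented as a comparison of two tests. Here confirmation is not required, and the rate falls under a comparative analysis. If groups in section 3.8 meant the two examination sequences, a test could be run, but it would not compare the examinations.

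A third reply is that other outcomes already expose the problem. Over-calling lowers endoscopy's specificity and PPV, and confirmed disease that endoscopy misses lowers its sensitivity. All of these are reported. This stands, and it limits the damage; it does not make this rate interpretable.

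Section 3.6 also has a sentence on validating accuracy by pathology or follow-up. It concerns the analysis of image features and is not tied to this rate.

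**Conclusion.** The point holds for this one secondary outcome. As worded, the lesion recognition rate cannot favour colposcopy, increases with over-calling by endoscopy, and leaves the planned comparison without a colposcopy figure. The direction of the bias needs only some discordant findings. Its size is uncertain: from about 41 of 212 participants with independent errors, through about 21 at correlation 0.5, towards 0, all under the assumptions listed in the working. Both examinations view the same cervix at the same time points, so some positive correlation is plausible.

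A reader might infer more than the protocol supports:
- **That colposcopy scores zero by definition.** This follows only if difficult means colposcopy-negative, which is not stated. On a looser reading colposcopy's rate is simply undefined.
- **That a particular false gain would be reported.** The same illustration gives 19% or 31% depending on the denominator, and less under correlation.
- **That two thirds of the extra calls are false positives.** They are not HSIL+, and only if the correlation is equal in both strata. Some could be confirmed low-grade lesions, which fall within the objective of detecting cervical and vaginal lesions.
- **That the trial cannot compare the two tests.** The primary accuracy outcome has a paired test with a 95% CI, and sensitivity and specificity are assessed by McNemar's test.

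**What to change.** Redefine the rate in section 3.7 for both examinations on histologically confirmed lesions at a stated threshold: the lesions marked by endoscopy (N + T) against those marked by colposcopy (Y + T), each over all confirmed lesions marked by either. Compare them with a paired method, clustered on participant if the analysis is by point, in place of the general chi-square wording of section 3.8.

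Report confirmed N-only and Y-only finds side by side. Beside them show the N-only and Y-only points below the threshold, with low-grade and benign histology separated, so that over-calling is visible for each examination.

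Section 3.6 provides for 2-4 tissue blocks in total and does not say that every marked point is sampled, so histology by point may be incomplete. State how specimens are linked to points, and report for each examination how many marked points have no histology.

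The Y, N and T points and the biopsy results are already collected. The cost is a change of definition, some linkage of specimens to points, a little more analysis, and probably a less favourable figure for endoscopy. The new rate partly overlaps with sensitivity, but it is relative: lesions that neither examination marks are outside it, and the protocol should say so. The primary outcome is unchanged.
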